- Data from the shared EHR of Fairview and UMP will be used for analysis. These data are already collected as part of clinical care, and the research team will access these data via the University of Minnesota's Informatics Consulting Service. The data that the Informatics Consulting Service already has on hand will be augmented with additional EHR data on the activation of the study's EHR alerts and the engagement with these alerts, along with data from the legacy HealthEast (which is now part of Fairview) Epic system which are not currently received by the Informatics Consulting Service. Fairview IT will share those data with the Informatics Consulting Service, who will merge it with the other EHR data that the Informatics Consulting Service already has. All of these data will be stored and accessed only on the ICS's secure data shelter.
- We will conduct retrospective chart reviews of the visit records for all visits where someone currently receiving a "high risk" opioid had an order that would reduce MME by no greater than 20% relative to the current prescription. The study team has already created the chart review tool that will be used. These chart reviews will ascertain whether there is any documentation of the clinical rationale for tapering that is consistent with the

CDC's guidelines. Each month during the 12-month study period, the study team will receive a new data extract from the AHC-IE, from which we will identify the relevant visits. We will record the Medical Record Number and visit date and store them in a database in the AHC-IE's server. At the conclusion of the 12 month study period, all of these files will be destroyed.

The PI will share that identifying information with the co-Investigator who will lead the chart reviews. For each visit that is reviewed, the study team will enter the information that is collected into a secure REDCap database. These data will then be shared with the ICS staff, who will link it to the EHR data in the ICS' secure data shelter.

- Data on the number of times per month each PCP checks the PMP, or has an assigned delegate check the PMP on their behalf, will be taken directly from the Minnesota PMP. The PMP data are held by the state of Minnesota Board of Pharmacy. The study team will email the PCPs in the study asking for electronic authorization to access their data on how frequently they and their delegates check the Minnesota PMP between August 2019 and September 2021.

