#### *Primary Outcome Analysis*

To test our primary hypotheses, we will fit mixed effects logistic regression models using data from the 12-month pre-intervention period, and the post-intervention period prior to any second-stage randomization (the model for the current “high risk” opioid group will be multinomial logistic regression due to the 3-category outcome). All models will include fixed effects for whether the encounter was at an intervention arm clinic, an indicator for whether the measurement was after the interventions began, and their interaction. The interaction is the primary measure of the intervention effect. These models include random effects for clinic and PCP (nested in clinic) to account for within-clinic and within-provider correlation. Because of the cluster-randomized design with a moderate number of clinics, residual imbalances in patient and PCP-characteristics among the randomized groups may exist. The primary analysis model will adjust for characteristics at all levels of the hierarchy including clinic-level (indicators for the four systems), PCP-level (clinician type [MD/DO, NP, or PA], sex, and length of tenure in medicine), and patient-level (age, sex, race/ethnicity, insurance status, and in-person or virtual visit). Separate models will be fit to assess the PDMP integration and choice architecture intervention and for the opioid-naïve and current, high-risk opioid users. In each model, the intervention group pools across two arms of the factorial design (e.g., the choice architecture intervention pools across arms 2 and 4) and the control condition pools across the remaining two groups (e.g., arms 1 and 3 to continue the example). A Bonferroni correction will adjust inference for multiple comparison across two different populations (opioid naïve and current, high-risk opioid users) but we will not adjust for multiple tests across the two different interventions.

As an exploratory analysis, we will assess whether PCP characteristics (clinician type and tenure in medicine) and patient characteristics (age, sex, and race/ethnicity) moderate the interventions’ effect. Tests for treatment effect heterogeneity will be implemented by adding the interaction between the potential moderator and the intervention indicator to the models for the primary

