#### *Secondary Outcomes Analysis: PDMP and Web Survey data*

For other EHR-derived secondary outcomes, we will use the same general modeling framework as for the primary outcome but will fit mixed effects logistic or linear models depending on whether the outcome was categorical or continuous.

To assess intervention effects on the frequency of checking the PDMP we will fit mixed effects Poisson regression models using data from the 12 months pre- and post-intervention. All models will include fixed effects for whether the PCP was at an intervention arm clinic, indicator for whether the month was during the intervention period, and their interaction. The models will adjust for clinician type, length of tenure in medicine, and health system indicators, and include random effects for clinic and PCP (nested in clinic) to account for within-clinic and within-provider correlation. As an exploratory analysis, we will assess whether PCP characteristics (clinician type and length of tenure) moderate the effect of the interventions using a similar process as the primary outcome.

A similar approach will be used for the web survey data, except we will fit mixed effect linear regression models using data from the pre- and post-intervention surveys. All models will include fixed effects for whether the PCP was at an intervention arm clinic, an indicator for whether the survey was the 12-month follow-up, and their interaction.

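### System and clinician covariates, listed without period interactions, barely touch the arm-by-period effect; system-specific change over time is left unadjusted

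*Combined protocol and SAP*

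**What the plan says.** Section 17.3, Primary Outcome Analysis, fits mixed logistic models (multinomial for high-risk users) to 12 pre-intervention months plus the post-intervention period. "All models will include fixed effects for whether the encounter was at an intervention arm clinic", together with a period indicator and the product of the two. "The interaction is the primary measure of the intervention effect". For clustering, "These models include random effects for clinic and PCP (nested in clinic) to account for within-clinic and within-provider correlation".

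The reason given for covariate adjustment is that, with a moderate number of clinics, "residual imbalances in patient and PCP-characteristics among the randomized groups may exist". The response is: "The primary analysis model will adjust for characteristics at all levels of the hierarchy including clinic-level (indicators for the four systems), PCP-level". The PCP characteristics named are type of clinician, sex and tenure, and the same sentence goes on to patient age, sex, race/ethnicity, insurance and in-person versus virtual visit.

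No covariate-by-period term is listed. The only covariate interactions mentioned are exploratory ones between a moderator and the intervention. The model for PDMP checking has the same form: "The models will adjust for clinician type, length of tenure in medicine, and health system indicators". Those covariates are all fixed, or nearly so, within a clinic or PCP.

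**The concern.** A covariate that is constant within a clinic or PCP adds the same amount to the log-odds before and after the start of the intervention. It can unbalance the arms in level, but a pre/post contrast has already removed level. What can disturb the interaction is a characteristic that is unequally spread over the arms and whose pre-to-post change differs. A main effect cannot represent that.

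The four systems are the obvious candidate. They are pooled in one analysis, and one feeds data from the "legacy HealthEast (which is now part of Fairview) Epic system" (section 5.2). If an arm happens to hold more clinics from a system whose prescribing changed for other reasons, part of that change is read as an intervention effect. The interval does not widen to allow for it, because the random effects, as naturally read, are intercepts. A reader of 17.3 could believe that imbalance at clinic level had been dealt with.

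**Working it through.** **1. The plan's own figures.** The documents give no figure for the effect of covariate adjustment, so the nearest check is the power section. Correlations of 0.025 and 0.075 on the logistic scale give variances of 0.025 × 3.290/0.925 = 0.0889 (clinic) and 0.050 × 3.290/0.925 = 0.1778 (PCP within clinic).

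- Exhibit 9 reproduces as a post-only contrast of 10 control against 30 intervention clinics: 81.5/89.7/95.0% and 77.5/86.5/92.8%, against the stated 81/89/95% and 77/86/93%.
- Exhibit 8 fits only a pre/post contrast (12 v 12 clinics, 12 + 6 months): 95.6/99.9/100/100% and 73.6/94.0/99.4/100%, against 96/100/100/100% and 76/95/100/100%. One cell is 2.4 points off.

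The variance components below are therefore close to those the plan used.

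**2. What each kind of covariate does.** Mixed logistic models were simulated with nested clinic and PCP intercepts.

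- From the power section: 48 clinics, 10 PCPs per clinic, 30 visits per month, a 7% rate. The true interaction was −0.174, a 15% reduction.
- From 17.3 and the power section: clinics pooled 24 v 24, 12 pre-months and 6 post-months.
- Assumed: covariate effects, degree of imbalance, shifts and turnover.
- 40 replicates per scenario.

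| Scenario | Interaction without the term | With the term |
|---|---|---|
| Forced system and PCP imbalance; add system + PCP main effects | −0.1686 (SE 0.030) | −0.1687 (SE 0.030) |
| 25% PCP turnover, extreme type mix; add system + PCP main effects | −0.183 | −0.174 |
| Shift of −0.2 in the over-represented system; add main effects | −0.237 | −0.237 |
| Same shift; add system × period | −0.237 | −0.169 |
| Virtual share 20→45% v 20→35%, odds ratio 0.5; add visit mode | −0.232 | −0.169 |

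With a stable PCP panel the main effects do nothing measurable. With extreme turnover they move the estimate by about 0.0085, a quarter of its standard error. Visit mode moves it by 0.063, or 0.063/0.174 = 36% of the effect.

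**3. Error rate under no effect.** Take 48 clinics, 24 v 24, 10 PCPs, 15 visits per month, 12 + 6 months and a 7% rate.

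- Sampling variance of one clinic's change: 1/(1800 × 0.0651) + 1/(900 × 0.0651) = 0.00853 + 0.01707 = 0.0256.
- Variance of the interaction: 0.0256 × (1/24 + 1/24) = 0.00213; SE 0.046.
- Variance added by system shifts of SD τ under unstratified allocation with assumed sizes 24/10/8/6: τ² × (48 − 776/48)/47 × (1/12) = 0.0564τ², where 776 = 24² + 10² + 8² + 6².
- Rejection rate: 2 × [1 − Φ(1.96 × √(0.00213/(0.00213 + 0.0564τ²)))].

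| τ (log-odds) | True SD (model SE 0.046) | Closed form | Clinic-level simulation | With system × period |
|---|---|---|---|---|
| 0.05 | 0.048 | 6% | about 6% | about 5% |
| 0.1 | 0.052 | 8% | 8% | about 5% |
| 0.2 | 0.066 | 17% | 16% | about 5% |
| 0.3 | 0.085 | 29% | 26% | about 5% |

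The closed form treats the contrast as exactly normal, which overstates the last row a little. Full mixed-model fits (300 null trials per setting) gave 9/20/27% for τ = 0.1/0.2/0.3 and 4–7% with system × period.

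**4. Does system × period suffice?** If the change varies between clinics within a system with SD σ, the added variance is σ²/12. For σ = 0.1/0.2/0.3 the same formula gives 10/22/36%. Adding system × period leaves these rates as they are. Estimating a between-clinic variance for change brings them to about 5%.

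**5. Price when systems do not differ.** Arm and system are correlated by chance with expected R² of 3/47 = 0.064. The standard error rises by a factor of about √(1/(1 − 0.064)) = 1.03. The mixed-model simulation gave about 4%.

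**The case against.** The strongest reply is that cancelling is what a pre/post contrast is meant to do: level imbalance is already gone, so the system and PCP main effects are redundant and harmless. That stands.

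A reader might infer that the planned adjustment as a whole is empty. The documents do not support that: the same sentence lists patient-level covariates that vary from visit to visit, and visit mode does real work whenever its mix shifts differently by arm. Change that acts through virtual visits is therefore partly covered already.

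A reader might also infer a biased trial. Clinics are randomised, so system-specific change adds variance over possible allocations. The harm is a chance distortion in the allocation actually drawn, with an interval that does not reflect it. A clinic-by-period random effect alone would restore the error rate to about 5%, even without system terms. That also stands, and it is why the fix contains both. The system terms additionally remove the distortion that the observed imbalance explains.

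The planned test of equal pre-intervention trends across arms and the monthly graphs are partial safeguards. The test looks only within the pre-period, and no action is tied to either.

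Finally, nothing in the documents shows that the systems' trends differ; a separate legacy record system is only a data-source fact. Section 5.1 does not mention stratification by system, but Exhibit 7, the randomisation plan, is not visible, so silence there does not establish unstratified allocation.

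**Conclusion.** The point holds in limited form. System indicators and time-constant PCP characteristics, as listed, leave the primary interaction and its standard error essentially unchanged. A system-specific pre-to-post shift therefore stays in the estimate, and the system × period terms remove it.

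The size depends on assumptions that are not in the documents: system sizes, shift SDs and unstratified allocation. The effect is trivial at a shift SD of 0.05 and material at 0.2, which is slightly larger than the 15% reduction of 0.174 log-odds.

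That only main effects are meant is the natural reading of 17.3, not an explicit statement. The multinomial and Poisson models share the structure but were not simulated.

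This is an inexpensive improvement, held with medium confidence. It is not a flaw that invalidates the analysis.

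**What to change.** In 17.3:

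1. Add system × period terms to the primary, EHR secondary and PDMP models. This takes 3 degrees of freedom, or 3 for each of the two logits in the three-category model.
2. Add a clinic × period random effect to the same models, so that the interval also covers clinic-level differences in change.
3. Keep the patient-level covariates, including visit mode, as planned.
4. Put clinician type × period in a pre-specified sensitivity analysis only.
5. State what the system and PCP main effects can and cannot correct, and whether randomisation was stratified by system.

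The cost is SAP wording, a standard error about 3–4% larger if systems do not differ in change, and a wider interval if clinics do.

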## 3.0 Study Endpoints/Events/Outcomes

### 3.1 Primary Endpoint/Event/Outcome:

**Opioid-Naïve Population:** Whether or not an opioid is prescribed in a primary care visit, *without* currently receiving a non-opioid alternative pain treatment (including a new order for a non-opioid pain treatment).

**Current Opioid-User Population:** A variable with three mutually-exclusive categories:

Category 1 (appropriate taper): Whether a primary care appointment with someone currently receiving a “high risk” opioid had an order that would reduce MME by no greater than 20%, relative to the current prescription, and there is documented evidence that the reduction was consistent with CDC guidelines. “High risk,” is defined as a patient is currently receiving opioids with >50 MME and/or currently receiving both an opioid and a benzodiazepine.

Category 2 (“inappropriate” taper): Whether a primary care appointment with someone currently receiving a “high risk” opioid had an order that would reduce MME without documented evidence that the reduction was consistent with CDC guidelines, or, decreased MME by greater amounts than recommended (>20% relative reduction in MME).

Category 3 (no taper): Whether a primary care appointment with someone currently receiving a “high risk” opioid had no reduction in MME.

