### 17.3 Statistical Analysis:

We will first empirically verify that randomization was successful by testing whether trends in the outcome are equal across the study arms in the 12 months prior to the start of the intervention period. Second, we will present descriptive statistics by intervention arm of the outcomes, basic characteristics of the PCPs, and clinical and demographic characteristics of the patients seeking care whose visits meet the inclusion criteria. We will also produce graphs of the unadjusted trends in the outcomes by month over the study period, and broken down by study arm.

We will run separate analyses for the opioid-naïve population and the current opioid user population. The analysis sample for the opioid-naïve population will be primary care visits for patients who have not had an active opioid prescription in the six months prior to the visit, and no cancer diagnosis in the 12 months prior to the visit. In order to identify the visits that plausibly might lead to an opioid prescription, we will restrict to primary care visits that have a recorded diagnosis that occurs regularly in opioid-prescribing visits. We are defining those diagnoses as diagnoses that were associated with at least a 3% opioid prescribing rate among opioid-naïve primary care visits across all FMG and UMP primary care clinics over a 12 month period and there were at least 25 opioid orders in visits with the diagnosis for all visits in the study clinics during the 12-month period before the study, excluding diagnoses for current opioid use, which is intended to have very high sensitivity for capturing chronic pain-related diagnoses, but low specificity. We have already created this list, which includes 294 specific diagnoses with pain-related diagnoses the most common.

The analysis sample for the current opioid user sample will be all primary care visits for patients with an active opioid prescription, excluding patients with a cancer diagnosis in the 12 months prior to the visit. We will include both in-person visits along with virtual (telephone or video) visits for all analyses.

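### The primary models leave out strong case-mix predictors the trial already holds and have no clinic-by-period term, so clinic-specific case-mix change adds noise and makes the confidence interval too narrow

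*Combined protocol and SAP*

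**What the plan says.** Section 17.3 (Primary Outcome Analysis) gives the adjustment set in full: health system; clinician type, sex and tenure; and "patient-level (age, sex, race/ethnicity, insurance status, and in-person or virtual visit". Its reason for adjusting is that "residual imbalances in patient and PCP-characteristics among the randomized groups may exist". The models are fitted "using data from the 12-month pre-intervention period, and the post-intervention period prior to any second-stage randomization", and "The interaction is the primary measure of the intervention effect". On clustering: "These models include random effects for clinic and PCP (nested in clinic) to account for within-clinic and within-provider correlation". No term lets a clinic's change between periods vary at random.

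The omitted variables are used elsewhere in the plan.

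- **Opioid-naïve visits.** Section 17.3 selects visits by "diagnoses that were associated with at least a 3% opioid prescribing rate among opioid-naïve primary care visits", and adds: "We have already created this list, which includes 294 specific diagnoses with pain-related diagnoses the most common". The diagnosis-specific rate is used only as an inclusion cut-off.
- **Current users.** Section 3.1 defines high risk as "currently receiving opioids with >50 MME and/or currently receiving both an opioid and a benzodiazepine", and splits tapers at a 20% relative reduction in MME. Current MME is therefore needed to score the outcome, and section 4.1 says the alert displays it. Neither MME nor the route into the high-risk group enters the model.

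Clinical characteristics of patients are only to be described by arm.

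**The concern.** Three per cent is the floor of the diagnosis list, and the plan itself says the list has low specificity. Diagnosis should therefore predict prescribing more strongly than most of the listed demographics. For current users, starting dose bears on the outcome category by arithmetic: removing one of n equal daily units cuts MME by 1/n, and anything above 20% is Category 2 whatever is documented.

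The effect is a difference in differences on the logit scale. If a clinic's mix of diagnoses, doses or routes changes between periods by an amount peculiar to that clinic, neither a covariate nor a random effect represents the change. It goes into the interaction as extra between-clinic variance that the model does not count. At stake are the precision of the primary estimate, the coverage of its interval and the false-positive rate.

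**Working it through.** **Inputs.** From section 17.2: 48 clinics in four equal arms and 10 providers per clinic. From Exhibit 8: a 7% control rate and 15 or 30 eligible visits per provider per month. From section 17.3: 12 pre-intervention months and pooling of two arms against two, so 24 v 24 clinics. I take 6 post months, because section 17.2 powers months 1–6. Bonferroni over two populations gives 0.05/2 = 2.5% two-sided (z = 2.241). The interim boundary is ignored.

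**Step 1: reproduce Exhibit 8.** The plan gives no formula. This one, in which clinic effects cancel between periods, matches:

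var = [2 / (k × 10 × m × p(1−p))] × (1/12 + 1/6), with p = 0.07 and k = 12 clinics per side.

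- m = 30: SE 0.0462. A 15% reduction is a log odds ratio of 0.1737, and power is Φ(0.1737/0.0462 − 1.96) = 96% (stated 96%).
- m = 15: SE 0.0653, power 76% (stated 76%). A 20% reduction gives 95% (stated 95%).

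All eight cells reproduce. Parallel-group versions that keep between-clinic variance gave 24–42% where the exhibit has 96%. On this reconstruction the stated power allows nothing for clinic-specific change.

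**Step 2: add clinic-specific drift.** Let δ be the SD across clinics of the pre-to-post change in case-mix logit. For 24 v 24 at m = 15:

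model variance = [2 / (24 × 10 × 15 × 0.0651)] × 0.25 = 0.002133 (SE 0.0462); true variance = 0.002133 + 2δ²/24.

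The true false-positive rate is 2[1 − Φ(2.241 × model SE / true SE)].

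| δ (assumed) | True SE | False positives at nominal 2.5% |
|---|---|---|
| 0 | 0.0462 | 2.5% |
| 0.04 | 0.0476 | 3.0% |
| 0.05 | 0.0484 | 3.2% |
| 0.09 | 0.0530 | 5.1% |
| 0.12 | 0.0577 | 7.3% |

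**Step 3: simulation (opioid-naïve, no true effect).** Both simulations assume ten diagnosis groups with rates of 3%–25%.

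| Drift SD 0.05 / 0.09 / 0.12 | Without diagnosis term | With it |
|---|---|---|
| Logistic model with clinic effects (2,000 trials per level) | 4.4 / 8.0 / 12.1% | 2.9 / 2.0 / 2.2% |
| Clinic-level difference in differences (1,500 runs) | 3.2 / 6.5 / 8.0% | 2.5 / 2.5 / 1.7% |

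In the first, the empirical SD without the term was 0.048 / 0.056 / 0.063 against a model SE of 0.044. Putting those SDs into step 2, δ = √[12 × (SD² − 0.044²)] = 0.066 / 0.12 / 0.156. Its labelled drift therefore acts like a somewhat larger δ, which explains why its rates are the highest. The pattern is the same in all three calculations.

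**Step 4: what cancels.** In a separate simulation with a 3% and a 15% diagnosis class, a 10-point mix shift common to both arms left the mean null interaction at 0.000. Clinic-specific shifts with SD 2.5 / 5 / 10 points also left it near zero, but gave 5.1 / 8.3 / 18.1% false positives at nominal 5%, against 4.3 / 5.3 / 4.8% with the diagnosis term.

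**Step 5: what the covariate leaves.** Suppose unmeasured clinic-by-period variation with SD 0.10 remains. With the diagnosis term, the true SD is √(0.046² + 2 × 0.10²/24) = 0.054 against a model SE of 0.046, and false positives are about 5.8% at nominal 2.5%.

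**Step 6: current users.** One of 2, 3, 4, 5 or 6 equal units is 50%, 33%, 25%, 20% or 17%. Up to four units the step exceeds 20%; from five it does not. The documents give no units per day by route, so this shows a mechanism, not a size.

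**The case against.** A reader might infer that any case-mix drift between periods biases the intervention effect. The documents do not support that. The post-period indicator absorbs drift shared by both arms, and the arm term and random intercepts absorb stable clinic differences. What remains is, under randomisation, noise.

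A reader might also infer that a change in route mix is known to move visits between appropriate and inappropriate taper. That needs low-dose benzodiazepine-route patients to take four or fewer units, which is nowhere stated; a patient above 50 MME could take two units, and a low-dose patient five or more.

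The strongest counter-argument is that the inflated error comes from the missing clinic-by-period random effect, and that the covariate looks like a full cure only because the simulations contain no other clinic-by-period variation. This stands, as step 5 shows. The covariate recovers precision by removing the measured part; the random effect makes the interval honest about the rest.

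Four further points stand in part.

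- The list rate is for any opioid order, whereas the primary outcome is an opioid without a non-opioid alternative. It is a proxy, so the adjusted simulation results are a best case.
- The simulations use clinic effects without the PCP level, so they are not exactly the planned model.
- The rates appear to come from the same 12 months as the model's pre-period, and the covariate may fit that period better than the later one.
- The plan already restricts to a fixed diagnosis list, adjusts for visit mode and checks pre-period trends by arm. These reduce the problem, but none represents a clinic's own change in mix.

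**Conclusion.** The point holds in limited form. The adjustment list omits diagnosis-specific rate, starting MME and high-risk route, all available to the trial, and the model has no place for case-mix change that differs between clinics. The result is lost precision and too narrow an interval, not systematic bias.

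The drift size is an assumption throughout. For the opioid-naïve model, drift SDs up to about 0.04 make little difference. At 0.05 false positives are about 3–4%, and at 0.12 about 7–12% (8.0% and 12.1% in the simulations, 7.3% in closed form), against a nominal 2.5%. These figures also rest on 24 v 24 clinics, 15 visits per provider per month, 12 and 6 months, and the assumed spread of diagnosis rates. No figure can be given for current users. The change is worth making because it is cheap and follows the plan's own reason for adjusting.

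**What to change.** In section 17.3, Primary Outcome Analysis:

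1. **Opioid-naïve model.** Add as a patient-level covariate the logit of the diagnosis-specific rate, frozen at its pre-study value. Preferably use the pre-study rate of the primary outcome itself rather than of any opioid order. State in advance how visits with several listed diagnoses are handled; a rule that takes the highest rate would depend on how many diagnoses are coded.
2. **Current-user model.** Add high-risk route (dose only, benzodiazepine only, both) and MME, measured at the start of each period and not at the visit, since visit-level values may already reflect the intervention. State a rule for patients not yet eligible at that date, and note that the benefit is unquantified.
3. **Both models.** Add a clinic-by-period random effect.
4. **Sensitivity analysis.** Report each model without the added covariates.

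The cost is SAP wording and a few derived variables from data already held. Visit diagnosis is recorded after randomisation, and adjustment changes the conditional odds ratio slightly (simulated log odds ratio −0.163 without the term, −0.172 with it), so both models should be shown. The random effect widens the interval where drift exists: at δ = 0.10 and 15 visits per month, valid power for a 15% reduction (two-sided 5%, 24 v 24) is 89% rather than 96%. That loss is already present in the planned analysis but not reported by it.
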